## STATEMENT OF COMPLIANCE

(1) [The trial will be carried out in accordance with International Council on Harmonisation Good Clinical Practice (ICH GCP) and the following:

- United States (US) Code of Federal Regulations (CFR) applicable to clinical studies (45 CFR Part 46, 21 CFR Part 50, 21 CFR Part 56, 21 CFR Part 312, and/or 21 CFR Part 812).

National Institutes of Health (NIH)-funded investigators and clinical trial site staff who are responsible for the conduct, management, or oversight of NIH-funded clinical trials have completed Human Subjects Protection and ICH GCP Training.

The protocol, informed consent form(s), recruitment materials, and all participant materials have been submitted to the IRB for review and approval. Approval of both the protocol and the consent form(s) was obtained before any participant was consented. Any amendment to the protocol was reviewed and approved by the IRB before the changes were implemented to the study. All changes to the consent form(s) were IRB approved.

## 1 PROTOCOL SUMMARY

### 1.1 SYNOPSIS

[figure not shown]
Title:	Random Assignment of Intervention Messages for Developing Personalized Decision Rules to Promote Physical Activity
Grant Number:	R01 HL142732
Study Description:	This study aims to develop a method for characterizing the dynamics of person-specific behavioral responses of a behavioral intervention. Our long-term goal is to evaluate a personalized adaptive messaging intervention for PA based on dynamical models of historical responses to intervention (and other inputs such as weather).
Objectives*:	Primary Objective: The aim of this project is to develop personalized dynamical models of physical activity (PA) under different weather and temporal conditions.
Endpoints*:	Primary Endpoint: change in minutes of moderate-to-vigorous physical activity following each of three types of micro-interventions on weekdays and weekends
Study Population:	80 female and male adults aged 18-29 years from the United States who engage in insufficient physical activity
Phase* or Stage:	Phase 1
Description of Sites/Facilities Enrolling Participants:	N/A
Description of Study Intervention/Experimental Manipulation:	Baseline education and self-regulatory training; provision of smartwatch that provides ad libitum behavioral feedback throughout study; 0-6 micro-intervention messages/day for 6 months
Study Duration*:	18 months
Participant Duration:	6 months

## 1.3 SCHEDULE OF ACTIVITIES

	Pre-Screening (Pre-consent)	Visit 1 Day 1	Intervention & Ambulatory monitoring	Visit 2 End of Month 6
Review Eligibility (questionnaires and accelerometer)	X			
Informed Consent		X		
Baseline assessment (demographics, motivation)		X		
Randomization		X		
Intervention			X	X
Adverse Events Reporting			X	X

## 2 INTRODUCTION

### 2.1 STUDY RATIONALE

Just-in-time adaptive interventions are a new strategy for delivering interventions to patients at moments when they are receptive and have an opportunity (or vulnerability) for behavior change. These interventions are often delivered using technology to reach people in the natural context of their daily lives. They require decision rules to specify which interventions are delivered, when they are delivered, and how often they are delivered. Our prior results raise questions about the sufficiency of a single decision rule for diverse populations. Those results showed that different people respond to different message content, responses varied on weekends and weekdays, and the timing and magnitude of responses varied. We seek to extend these results by collecting data on a larger sample of participants and enriching the model with additional data to reduce uncertainty. We focus on location-specific weather indices to enrich our models. Extensive data link physical activity with weather but, to the best of our knowledge, weather indices have never been used to inform physical activity intervention delivery. We will determine whether behavioral responses to text messages vary, for example, on sunny vs cloudy days, warm vs cool days, or rainy vs dry days. To achieve this aim, we need to collect intensive longitudinal data on behavioral responses to text messages under a variety of weather conditions.

### 2.2 BACKGROUND

Physical activity (PA) reduces the risk for cardiovascular disease, diabetes, and many cancers. Yet national data indicate that less than 5% of US adults attain the recommended level of PA, and activity levels consistently decrease across adulthood. Physical inactivity is also part of a constellation of lifestyle factors – with smoking and diet – that contribute to weight gain in early adulthood. This developmental period is critical because risk factors that compromise cardiovascular health begin to accumulate. Interventions that prevent decreases in PA during this time can reduce long-term chronic disease risk.

Young adults often elude preventive health interventions because they are often underinsured and do not have consistent contact with health care systems. Technological advances have made it possible to reach this segment of the population and shown promise for increasing PA. For example, short message service (SMS) interventions, have shown a consistent positive effect on PA. Yet efforts to increase SMS intervention effects via tailoring, targeting or personalizing have not realized their potential. Other approaches have emerged for tailoring interventions based on treatment responses or contextual factors that increase vulnerability/ opportunity (e.g., stepped care, just-in-time adaptive interventions). The decision rules in these approaches are assumed to generalize across the population (i.e., one rule for all participants). But behavior is complex and multiply determined so it is possible that treatment responses are idiosyncratic, necessitating personalized decision rules. Existing approaches also fail to capitalize fully on the rich information from the intensive longitudinal data available from pervasive wearable sensors. Building on interest in precision medicine, we propose a method to develop personalized adaptive messaging interventions using tools from control systems engineering (system identification and robust control synthesis). This approach can ensure that an individual only receives content to which s/he

responds when s/he is likely to respond and only as often as needed to achieve specified behavioral goals. Our long-term goal is to evaluate a personalized adaptive messaging intervention for PA based on dynamical models of historical responses to intervention (and other inputs such as weather).

## 2.3 RISK/BENEFIT ASSESSMENT

### 2.3.1 KNOWN POTENTIAL RISKS

Participants may find the Actigraph activity monitor worn at the waist for the run-in part of the study, uncomfortable. Participants may find wearing a Fitbit Versa slightly uncomfortable or bulky if they do not usually wear a watch. Both devices may be removed when showering/bathing. There may be some mild discomfort associated with answering some of the interview or survey questions. The participants will be instructed that they have the right to refuse to answer any questions that they find too uncomfortable. There may be a risk of feeling self-conscious or embarrassment when receiving message notifications on their smartphone. Participants will be instructed not to answer any notifications when it is not safe to do so (e.g. driving, attending meeting at work) and that the message be available for acknowledgment within 30 minutes if their situation should change. The small amount of compensation associated with the acknowledgment (\$0.25) will not persuade the participant to risk their safety to respond to the message. The app collects data on the participant's location and the weather conditions at this location when messages are received and acknowledged to determine their impact on your physical activity levels at any given time throughout your day. Participants may find the disclosure of their location unsettling. There is a slight risk of soreness if physical activity is increased in sedentary participants. Participants will be given information regarding progressive adaption to minimize this risk.

There is a risk of loss of confidentiality if your information or your identity is obtained by someone other than the study team, but precautions will be taken to prevent this from happening and all information obtained from this research will be kept as confidential as possible. Code numbers rather than names will be used on all research records and the information linking these codes to the participants' identities will be kept separate from the research records. The confidentiality of the electronic data created by participants or the researchers will be maintained to the degree permitted by the technology used and is securely encrypted at all stages of the study. Despite our best efforts, it is not possible to guarantee absolute confidentiality.

### 2.3.2 KNOWN POTENTIAL BENEFITS

There is no guarantee that participants will benefit from this research. The possible benefits that participants may experience from the interventional research study include increasing their physical activity and associated health benefits.

The research may lead to the creation of personalized interventions that create long-term behavior changes in physical activity levels for young adults.

### 2.3.3 ASSESSMENT OF POTENTIAL RISKS AND BENEFITS

Risks involved low severity and low likelihood, and were outweighed by potential benefits of the knowledge gained.

### 3 OBJECTIVES AND ENDPOINTS

*Provide a description of the study objectives and endpoints, as well as a justification for selecting the particular endpoints, in the table format included below. This will provide clear articulation of how the selected primary and secondary endpoint(s) are linked to achieving the primary and secondary objectives and an explanation of why endpoint(s) were chosen. Data points collected in the study should support an objective or have a regulatory purpose. Therefore, careful consideration should be given prospectively to the amount of data needed to support the study's objectives.*

*An **objective** is the purpose for performing the study in terms of the scientific question to be answered. Express each objective as a statement of purpose (e.g., to assess, to determine, to compare, to evaluate) and include the general purpose (e.g., feasibility, acceptability, engagement of the intervention target, identifying mechanisms of action, mediation, moderation, efficacy, effectiveness, dissemination, implementation).*

*A study **endpoint** is a specific measurement or observation to assess the effect of the study intervention. Study endpoints should be prioritized and should correspond to the study objectives and hypotheses being tested. Give succinct and precise definitions of the study endpoints used to address the study's primary objective and secondary objectives (e.g., specific diagnostic tests that define safety or efficacy, clinical assessments of disease status, assessments of psychosocial characteristics, patient reported outcomes, behaviors or health outcomes). A full description of study endpoints, including administration, scoring, psychometrics, adjudication of endpoints, etc., belongs in **Section 8, Study Assessments and Procedures**.*

*A putative mechanism of action is the theorized explanation for how the intervention functions.*

*Consider whether primary and secondary endpoints should be adjusted for multiple comparisons, family-wise error rates, alpha inflation, etc. Details of any such adjustments should be included in **Section 9.4.2, Analysis of the Primary Endpoint(s)** and **Section 9.4.3, Analysis of the Secondary Endpoint(s)**.*

OBJECTIVES	ENDPOINTS	JUSTIFICATION FOR ENDPOINTS	PUTATIVE MECHANISMS OF ACTION
Primary			
Develop and test method for estimating person-specific effects of micro-interventions on health-enhancing physical activity.	Change in moderate(or higher) physical activity duration following message receipt	Moderate-to-vigorous intensity physical activity is health enhancing.	N/A

OBJECTIVES	ENDPOINTS	JUSTIFICATION FOR ENDPOINTS	PUTATIVE MECHANISMS OF ACTION
	is the primary endpoint		

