### 4.2 SCIENTIFIC RATIONALE FOR STUDY DESIGN

This design was selected to evaluate the heterogeneity of person-specific responses to treatment.

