## 9.2 SAMPLE SIZE DETERMINATION

Statistical power analysis is not relevant for estimating person-specific dynamic models. Our proposed sample size (n=80) is based on the upper limit for phase 1 clinical trials and will enable us to capture the heterogeneity of PA dynamics and estimate model uncertainty within the resource constraints of early stage intervention development work.

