## 9.4 STATISTICAL ANALYSES

### 9.4.1 GENERAL APPROACH

The steady state response (i.e., final cumulative response) to each type of intervention message will be recorded as the primary outcome variable. The mean and standard deviation of steady state responses will be calculated.

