### 9.4.2 ANALYSIS OF THE PRIMARY ENDPOINT(S)

System identification will be used to estimate coefficients for person-specific dynamic models of moderate-to-vigorous physical activity durations in 15-minute epochs. Model coefficients will be used to simulate expected responses to each type of micro-intervention (separately for weekdays and weekends). Steady state responses for each message type on weekdays and weekends will be extracted as the primary outcome. An independent-sample t-test will be used to evaluate whether the average steady state response to each message type on weekdays and weekends differs significantly from zero.

---

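### The planned SD of simulated responses cannot be read as heterogeneity, because the plan specifies no person-level uncertainty or validation

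*Combined protocol and SAP*

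**What the plan says.** The primary objective in Section 3 is "Develop and test method for estimating person-specific effects of micro-interventions on health-enhancing physical activity". Section 4.2 adds: "This design was selected to evaluate the heterogeneity of person-specific responses to treatment".

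The analysis runs in three steps.

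- Section 9.4.2: "System identification will be used to estimate coefficients for person-specific dynamic models of moderate-to-vigorous physical activity durations in 15-minute epochs".
- Section 9.4.2: "Model coefficients will be used to simulate expected responses to each type of micro-intervention", separately for weekdays and weekends. Three message types and two day types give six responses per person.
- Section 9.4.2 then uses a t-test to "evaluate whether the average steady state response to each message type on weekdays and weekends differs significantly from zero". Section 9.4.1 adds: "The mean and standard deviation of steady state responses will be calculated".

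The nearest text to a person-level check is in Section 9.2, which says that 80 participants "will enable us to capture the heterogeneity of PA dynamics and estimate model uncertainty". No method, criterion or output follows from it. Secondary endpoint, subgroup, individual-data and exploratory analyses (9.4.3, 9.4.7, 9.4.8, 9.4.9) are all marked N/A. Model order, number of message lags, fit criterion and any division of the data for validation are not given.

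**The concern.** The claim of interest is about individuals, but every planned output is a group summary of model output. Each personal response is an estimate, and nothing in the plan says how precise it is. The SD of 80 such estimates is positive even if messages do the same thing, or nothing, in everyone. A reader who takes that SD as the answer to Section 4.2 would be reading noise and signal together.

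This matters for later use. Section 2.2 describes choosing each individual's content and timing from his or her own model, and Section 1.1 names a personalised intervention as the long-term goal. Whether personalisation is worth pursuing depends on how much people truly differ, and the plan as written does not isolate that quantity.

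**Working it through.** **No figure to reproduce.** Section 9.2 gives n = 80 without effect size, SD, alpha or power. The point is one of omission, with simulation used only to illustrate its size.

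**What the SD contains.** Write person i's estimated response as the true response plus estimation error. If the two are independent, then

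observed variance = τ² + average of sᵢ²,

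where τ is the true between-person SD and sᵢ is person i's standard error. The plan reports the left side only.

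**Data behind each estimate.** The payment terms in Section 5.5 imply (85 − 40)/0.25 = 180 acknowledged messages in each of the first two two-month blocks and (100 − 55)/0.25 = 180 in the third. That is 540 per person, or 540/182 = 2.97 per day. This is inferred from payment ceilings, not stated. With the 40/40/20 mix of Section 4.1, Move More has 216 messages, of which 216 × 2/7 ≈ 62 fall on weekends. Inspirational Quotes has 108, of which about 31 fall on weekends.

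**Null simulations.** The following are assumed: an ARX model with two autoregressive lags, 4 or 8 message lags, 64 waking epochs per day, 182 days, and 0 to 6 messages per day. The steady state response is the sum of the message coefficients divided by (1 − a₁ − a₂). The true effect is zero in all 80 people.

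| Run | Range of SD over the six responses (min) |
|---|---|
| 8 lags, first activity model | 0.15 to 0.41 |
| 4 lags, 3% chance per epoch that activity starts | 0.31 to 0.68 |
| 8 lags, 3% chance | 0.50 to 1.00 |
| 8 lags, 6% chance | 0.62 to 1.39 |
| Run that also kept each person's standard error | 0.47 to 1.03 |

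In the second to fourth runs, 40% to 54% of people had a positive estimate for a given response. All 18 tests of a group mean against zero were non-significant (p from 0.07 to 0.97).

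**The split recovers the truth.** In the last run the root mean square standard error was 0.46 to 1.07 min. If the lowest values belong together, and likewise the highest (an assumption), then 0.47² − 0.46² = 0.009, so τ ≈ 0.10. At the top, 1.03² − 1.07² = −0.08, so τ is set to 0. Nearly all the spread was estimation error.

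**When people do differ.** Take a true SD of 0.5 min. With error SD 0.15, the reported SD would be √(0.25 + 0.0225) = 0.52. With error SD 1.39, it would be √(0.25 + 1.932) = 1.48, and only 0.25/2.182 = 11% of the variance would be real. In a simulation with true mean 0.5 and SD 0.5, personal estimates correlated 0.57 to 0.83 with the truth. Under the model above, the true share of variance is then 0.57² = 0.32 to 0.83² = 0.69.

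**Sensitivity of a held-out check.** The number of people out of 80 whose held-out prediction improved when message inputs were added, in two separate simulations:

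| True cumulative effect per message | Simulation A | Simulation B |
|---|---|---|
| Zero | 3 | 2 |
| 0.5 min in everyone | 10 | not run |
| 1 min in everyone | 27 | 14 |
| Real differences (A: mean 0.5, SD 0.5) | 16 | 9 |

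Simulation A trained on the first three quarters of follow-up. Messages occupy about 3 of 64 epochs a day, so epoch-by-epoch prediction error responds little to them. Even with a real 1-minute effect in everyone, most people showed no improvement.

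**The case against.** The strongest reply is that the plan does test something. Sections 4.1 and 9.1 state a null hypothesis about the effect of messages on activity, and Section 9.4.2 tests it on the average. Section 4.1 places the trial in Phase 1, with the aim of developing a method, and evaluation of a personalised intervention lies beyond it. This stands. A reader might infer that the primary objective goes wholly unanswered, but the documents do not equate testing the method with predicting unseen behaviour. What is missing is the person-level part.

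A reader might also infer that noisy personal models undermine the t-test. They do not. Message schedules are randomised within person, so estimation noise does not by itself bias the mean, and the standard error of the mean properly uses the total variance, error included.

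Nor would the plan present noise as named responders. It classifies nobody, and Section 9.4.8 provides no individual tabulation. The exposure is confined to the SD.

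Finally, validation may be intended as part of system identification. That is possible, but the plan does not say so, and an unstated check can be chosen after the results are seen. The stated intention in Section 9.2 to estimate model uncertainty has no procedure attached.

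**Conclusion.** The point holds in this limited form. The plan reports a between-person SD with nothing to separate estimation error from true differences, so its outputs do not answer the heterogeneity question in Section 4.2 or the person-specific part of the objective in Section 3. The group-mean test stands.

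With zero effect in everyone, the simulated SD ran from about 0.15 to 1.4 min. This range rests on assumed model order, lags, waking hours, message frequency and activity rates, none of which the plan fixes. The direction is firm because it follows from the variance identity; the size is illustrative.

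A reader might infer that counting people with better held-out prediction would settle the matter. The simulations argue against it, since that count would dismiss many real effects. The change should be made, but its absence is not fatal to the trial.

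**What to change.** Amend Section 9.4.2 as follows.

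1. Report a standard error or interval for each person's steady state response, for each message type and day type. A bootstrap over whole days or weeks is one option, since 15-minute activity counts are unlikely to give well-behaved residuals. Standard errors that are too small would leave error in the heterogeneity estimate.
2. For each of the six responses, fit a random-effects model to the personal estimates with their standard errors. Report the true between-person SD (τ) with an interval as the measure of heterogeneity. The raw SD can stay as a description.
3. As a supporting check, fit and select model order on a pre-specified part of each person's follow-up, for example alternating weeks. Report held-out prediction error with and without message inputs. State that this check has low sensitivity at plausible effect sizes and that the count of people improved will not be used to classify responders.
4. Keep the primary steady state estimates on all data.

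No new participants, data or procedures are needed. The cost is analysis time, plus a reported heterogeneity figure that is likely to be smaller than the raw SD.

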## 4 STUDY DESIGN

### 4.1 OVERALL DESIGN

This single-site trial is in Phase 1 of behavioral intervention development with the goal of developing a method for optimizing person-specific intervention dosing to promote health-enhancing physical activity. To test the null hypothesis that each message type will not lead to increased moderate-to-vigorous physical activity, we use a within-person randomized trial design. All participants received 0-6 messages/day drawn from three content libraries (Move More, Sit Less, Inspirational Quotes). The number of messages and content source for each message was determined randomly for each participant every day. The allocation ratio was set so participants would receive approximately 40% Move More messages, 40% Sit Less messages, and 20% Inspirational Quote messages. Randomization was conducted automatically by custom software developed to deliver messages. This intervention is referred to as Random Assignment of Intervention Messages (Random AIM).

